Cover Page

Official Study Title: Three Approaches to Maintenance Therapy for Chronic Insomnia in Older Adults

NCT Number: NCT03774810

Date: 04/12/2022

The Effects of Solriamfetol and CBT-I (alone and in combination) on Sleep Continuity, Sleepiness, Fatigue, and Performance in Patients with Insomnia Disorder.

Principal Investigator	[name] Department of Psychiatry [name] [contact] or [contact] [contact]
Regulatory Sponsor	This work is supported by Axsome Pharmaceuticals
NIH Grant Number	N/A
Investigational Product:	Solriamfetol
Protocol Number:	850945
IND/ IDE Number: [If applicable]	N/A
ClinicalTrials.gov Number	In process
Title	The Effects of Solriamfetol and CBT-I (alone and in combination) on Sleep Continuity, Sleepiness, Fatigue, and Performance in Patients with Insomnia Disorder.
Short Title	Solriamfetol and CBT-I
Study Summary	Medication is FDA approved. The objective of this project is to test the efficacy of solriamfetol for treating insomnia (alone and in combination with CBT-I). Ultimately, this study will test whether wake extension (regardless of how it is achieved) will consolidate sleep and improve sleep continuity.
Methodology	Please see investigational plan for more information
Study Duration	12-18 months
Study Center(s)	One site only: Penn Behavioral Sleep Medicine Program
Objectives	
1. To investigate the effects of solriamfetol on sleep continuity, alone and in combination with CBT-I.2. Assess the effects of solriamfetol on daytime sleepiness, fatigue, adherence with “sleep rescheduling”, and on daytime performance
Number of Subjects	We will enroll and complete 40 subjects with Insomnia Disorder (60 recruited and a min. of 40 completed subjects).

Main Inclusion and Exclusion Criteria	Subjects. Subjects will be between the ages of 25-65 years old and have a stable sleep/wake schedule (no shift work) with a preferred sleep phase between 9:00 PM and 9:00 AM.
	Inclusion Criteria. Adults ≥ 25 and ≤ 65 years of age with chronic insomnia who meet DSM-5 criteria for Insomnia Disorder and ICSD-3 criteria for Psychophysiological insomnia. In addition, all subjects will have a sleep initiation and/or a sleep maintenance complaint (≥ 30 min. to fall asleep and/or ≥ 30 min. of wakefulness during the night) with a problem frequency ≥ 3 nights/wk and problem duration ≥ 3 mo. This profile must be evident at both intake (based on retrospective reports) and as an average profile from the two weeks of baseline diaries (based on prospective sampling).
	Exclusion Criteria for All Subjects. In brief, the exclusionary criteria are currently in treatment for insomnia, unstable medical or psychiatric illness, night shift work, and/or a history of other sleep disorders.
Investigational Product (drug, biologic, device, etc.)	Solriamfetol (trade name: Sunosi), 75mg.
Duration of administration (if applicable)	4 weeks
Reference therapy	Cognitive Behavioral Therapy for Insomnia (CBT-I)
Statistical Methodology	A 2x2 mixed model design. The two factors will be 1) treatment (+/- solriamfetol and +/- CBT-I) and 2) Time (pre-post assessment, with additional follow-up data).
Safety Evaluations	Daily diary assessments of side effects, weekly symptom checklists to monitor the health status of subjects (upon disbursement of medication). We will utilize a side-effect check list based on the package insert for Solriamfetol.
Data and Safety Monitoring Plan	We will establish a four-person advisory board comprised of a second MD sleep medicine specialist, a clinical psychologist, a nurse sleep scientist, and a biostatistician. Membership consists of persons completely independent of the investigators who have no financial, scientific, or other conflicts of interest with the trial. Collaborators of the PIs will not be eligible to serve on the advisory board. The board will receive reports from the study team every six months with information about the progress of recruitment, the demographic characteristics of participants, serious adverse events, the number of dropouts, and participants' reasons for dropping out, and any protocol amendments. These meetings will focus on the conduct and progress of the study, including participant accrual, protocol compliance, and problems encountered.

BACKGROUND AND STUDY RATIONALE

1. Introduction

Background and Relevant Literature

Presently, treatment for insomnia (in the case of cognitive behavioral treatment for insomnia [CBT-I]) focuses on limiting time in bed to reduce night-time wakefulness, thereby improving sleep continuity and daytime performance. The proposed project approaches insomnia treatment differently: the same outcomes may be achieved by enhancing and/or extending wakefulness during the day. The current proposal will test whether enhancing daytime wakefulness using a wake-promoting medication, solriamfetol, can improve sleep continuity and daytime performance, both as a stand-alone and in combination with CBT-I.

The current pharmacological approach for the treatment of insomnia is largely sedative medications, which promote sleep and have some benefit, but considerably limited efficacy compared to cognitive behavioral treatment for insomnia (CBT-I). Part of the mechanism of action for CBT-I is that over the course of 2-6 weeks of behavioral treatment, time in bed is severely limited, which has the intended outcome of increasing homeostatic sleep drive and thereby reducing night-time wakefulness. The current unknown is whether implementing this mechanism via wake-promoting medication can achieve efficacious outcomes. It is expected (given a common mechanism [wake extension]) that both CBT-I and treatment with solriamfetol [SFTRL] will improve sleep continuity, and that such effects will potentially be additive. Preliminary work by our group with another wake promoting medication suggests that such outcomes are feasible (PMID: 15283007). If successful, this unique treatment approach may provide an important alternative for patients that do not tolerate sleep restriction during CBT-I or for whom the transient iatrogenic sleepiness of CBT-I represents an unacceptable risk (e.g., surgeons, pilots, etc.).

2. Name and Description of the Investigational Product

Solriamfetol (trade name Sunosi), is a norepinephrine-dopamine reuptake inhibitor available in 75mg and 150mg tablets for oral administration during the day. Solriamfetol's primary indication is to treat excessive daytime sleepiness (EDS) in patients diagnosed with OSA or Narcolepsy. It binds to the dopamine transporter and the norepinephrine transporter with affinities (K_i) of 14.2 μ M and 3.7 μ M, respectively), does not undergo significant metabolism in humans, and has a T_{max} of ~2 hours (range 1.25–3.0 hours) and a $T_{1/2}$ of ~7.1 hours. The pharmacokinetic profile of solriamfetol, along with the absence of active metabolites, makes it unlikely that there are accumulation effects with multiple doses over days. See the attachment for a copy of the package insert for solriamfetol.

Solriamfetol will be provided by Axsome Pharmaceuticals (no cost), and managed by, the Investigational Drug Services of the University of Pennsylvania. An over encapsulation technique will be used to ensure that the drug doses and placebo formulations appear identical. The first five participants will be enrolled slowly to observe whether any adverse responses occur (e.g., taking longer to fall asleep after medication administration at 2pm) that would necessitate protocol modifications, for instance to the timing of medication dosing, if not amount.

Solriamfetol or placebo will be administered at 2pm daily for 4 weeks. Dosage will (for all subjects) start at 75mg. This dosage was chosen through weighing up the need to extend wake/delay bedtime to consolidate sleep and improve sleep continuity (necessitating a later timing of dose than typical), without inadvertently enhancing wake to the point where it extends sleep latency. Rather than downwardly titrate the medication, the timing of dosing will be altered where required (for example, timing advanced to 1pm or 12pm). Changes in dose timing will occur when the study staff (therapist, PI, and medical collaborator) deem it to be optimal (i.e., in response to extended sleep latency). Subjects in the SRFT + CBT-I arm will also be eligible for changes in dose timing if they report being unable to adhere to the prescribed time to bed (PTTB) component of CBT-I. As noted above, medication use will also include a 1-week placebo run-in and a 3-week placebo "run-out" (eight weeks' total). The timing of the first administration of SRFTL will (for those receiving CBT-I) align with the start of sleep restriction (Session 2).

All study medication will be provided by Axsome Pharmaceuticals (no cost) and will be received, stored, and packaged by the University of Pennsylvania Investigational Drug Service (IDS). IDS will create blister packs for each patient that are identical and will allocate active medication and placebo according to treatment condition. This will enable double blinding of the study. All doses will be over-encapsulated, and all daily doses will be delivered as a single capsule. The use of blister

packs will also allow us to not only track adherence but to identify the patterning of medication use. Blister packs will be returned once a month when subjects will be evaluated and provided the next month's medication supply. The study CRC will dispense and receive the foil packs. The pattern of used and unused data will be coded.

2.1 Nonclinical and Clinical Data To Date

The use of solriamfetol to treat EDS has been evaluated and extensively profiled in the literature. Given the shared EDS phenotype between narcolepsy, OSA, and insomnia, such data support that solriamfetol may be useful in those patients who cannot or do not tolerate the iatrogenic effects of sleepiness in CBT-I. Three such studies are listed below:

Krystal, A. D., Benca, R. M., Rosenberg, R., Schweitzer, P. K., Malhotra, A., Babson, K., ... & Strohl, K. P. (2022). Solriamfetol treatment of excessive daytime sleepiness in participants with narcolepsy or obstructive sleep apnea with a history of depression. *Journal of psychiatric research*, 155, 202-210.

Servid, S. (2012). New Drug Evaluation: solriamfetol tablets, oral.

2.2 Human Pharmacokinetics The time to peak levels of solriamfetol is about 2 hours (range 1.25–3.0 hours). Solriamfetol is minimally metabolized in humans. Its elimination half-life is about 7.1 hours.

2.3 Clinical Studies in Adults Please see section 1.2.1

2.4 Clinical Studies in Children N/A

2.5 Dose Rationale (if applicable) 75mg was chosen through weighing up the need to extend wake/delay bedtime to consolidate sleep and improve sleep continuity (necessitating a later timing of dose than typical), without inadvertently enhancing wake to the point where it extends sleep latency. Rather than downwardly titrate the medication, the timing of dosing will be altered where required (for example, timing advanced to 1pm or 12pm). Changes in dose timing will occur when the study staff (therapist, PI, and medical collaborator) deem it to be optimal (i.e., in response to extended sleep latency). Subjects in the SRFT + CBT-I arm will also be eligible for changes in dose timing if they report being unable to adhere to the prescribed time to bed (PTTB) component of CBT-I.

3 Study Objectives

As noted above, the current proposal is for a one-year study to investigate whether solriamfetol can improve sleep continuity and daytime performance, alone and in combination with CBT-I. It is expected (given a common mechanism [wake extension]) that both CBT-I and treatment with solriamfetol will improve sleep continuity, and that such effects will potentially be additive.

3.1 Primary Objective(s)

To investigate the effects of solriamfetol on sleep continuity, alone and in combination with CBT-I.

3.2 Secondary Objectives (if applicable)

Assess the effects of solriamfetol on daytime sleepiness, fatigue, adherence with “sleep rescheduling”, and on daytime performance

4. Investigational Plan

All subjects will be monitored for 2 weeks prior to treatment, for 8 weeks during treatment, and for 2 weeks following treatment. Additionally, subjects will complete two questionnaires complete two questionnaires (Insomnia Severity Index [ISI] and Retrospective Sleep Continuity Assessment Questionnaire [RSCAQ]) 3 months after completing treatment.3 months after completing treatment. Subjects receiving solriamfetol will take medication at 2pm daily for 4 weeks. Medication use will also include a 1-week placebo run-in and a 3-week placebo “run-out” (8 weeks’ total). Note: This design was used for our prior trials of CBT-I with wake promoting medications. Subjects receiving CBT-I will have 8 weekly

sessions (up to 90 minutes in duration). Daily sleep diaries will be administered to assess for differences in sleep continuity between conditions and over time. Self-report weekly assessments will also be administered and will include standard retrospective measures of insomnia (ISI), sleepiness (Epworth Sleepiness Scale, ESS), depression (PHQ-9), fatigue (Functional Assessment of Chronic Illness Therapy – Fatigue Scale [*FACIT-Fatigue*]), PROMIS-Short Form 7a, and Brief Fatigue Inventory [BFI]), treatment acceptability (MITAS)), and daytime function (Functional Outcomes of Sleep-10 item, FOSQ-10). Daytime function will also be objectively assessed daily via Ecological Momentary Assessment and at the end of baseline treatment, and post treatment periods using a PVT phone-based app. Self-report assessments will be accomplished on-line via RedCap software and subjects will also be asked to complete weekly and monthly questionnaires via Hypknowledge (a PHT Penn Health Tech Clinical Research Tool) site.

Treatment Regimen (as noted above)

The first five participants will be enrolled slowly to observe whether any adverse responses occur (e.g., taking longer to fall asleep after medication administration at 2pm) that would necessitate protocol modifications, for instance to the timing of medication dosing, if not amount.

Medication: Solriamfetol (SRFTL) or placebo (PLA) will be administered at 2pm daily for 4 weeks. Dosage will (for all subjects) start at 75mg. This dosage was chosen through weighing up the need to extend wake/delay bedtime to consolidate sleep and improve sleep continuity (necessitating a later timing of dose than typical), without inadvertently enhancing wake to the point where it extends sleep latency. Rather than downwardly titrate the medication, the timing of dosing will be altered where required (for example, timing advanced to 1pm or 12pm). Changes in dose timing will occur when the study staff (therapist, PI, and medical collaborator) deem it to be optimal (i.e., in response to extended sleep latency). Subjects in the SRFT + CBT-I arm will also be eligible for changes in dose timing if they report being unable to adhere to the prescribed time to bed (PTTB) component of CBT-I. As noted above, medication use will also include a 1-week placebo run-in and a 3-week placebo “run-out” (eight weeks’ total). The timing of the first administration of SRFTL will (for those receiving CBT-I) align with the start of sleep restriction (Session 2).

All study medication will be provided by Axsome Pharmaceuticals (no cost) and will be received, stored, and packaged by the University of Pennsylvania Investigational Drug Service (IDS). DS will create blister packs for each patient that are identical and will allocate active medication and placebo according to treatment condition. This will enable double blinding of the study. All doses will be over-encapsulated, and all daily doses will be delivered as a single capsule. The use of blister packs will also allow us to not only track adherence but to identify the patterning of medication use.

Cognitive Behavioral Therapy: Treatment will be conducted by a master therapist via a HIPAA compliant video link (Zoom), with 1-2 members of our established cohort of CBT-I experts (n=17) serving as backup therapists. Sessions 1-8 will follow our published protocol (published in 2005 by Springer). Each session will be conducted individually and have a singular focus per session. All sessions following the delivery of sleep restriction therapy & stimulus control instructions (post Session 2) will include, as needed, management of non-adherence and/or time-in-bed titration. The Session specific itinerary will be as follows.

Session 1: evaluation and orientation

Session 2: data acquisition and delivery of sleep restriction therapy & stimulus control instructions

Session 3: review of sleep hygiene

Session 4: management of non-adherence and/or time-in-bed titration only

Session 5: cognitive therapy [de-catastrophization]

Session 6: management of non-adherence and/or time-in-bed titration only

Session 7: management of non-adherence and/or time-in-bed titration only

Session 8: review of treatment progress and relapse prevention.

All treatment will be delivered by a single master therapist ([name] PhD CBSM). [name] has more than 27 years’ experience with CBT-I, he is one of the authors of our published treatment manual (1), and he is also a co-author of a second CBT-I treatment manual (2). He was a consultant for the VA’s rollout of CBT-I, he jointly conducts the Penn 3-day Basic and Advanced CBT-I courses, and he regularly conducts on-site one-day CBT-I workshops. As a final testament to his expertise, he was one of the first individuals to be certified in behavioral sleep medicine and one of the first to receive the SBSM’s Distinguished Career Achievement Award.

5. General Design

A double blind 2x2 mixed model design. The two factors will be 1) treatment (+/- solriamfetol and +/- CBT-I) and 2) Time (pre-post assessment, with additional follow-up data). Patients with insomnia will be randomly assigned to treatment condition.

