5.4 Follow Up Phase

Three months after completion of treatment, subjects will complete two questionnaires (Insomnia Severity Index [ISI] and Retrospective Sleep Continuity Assessment Questionnaire [RS-CAQ]).

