To ensure that the clinical effects observed in this study are not obscured by other medications

Inadequate language comprehension

Assessed informally by the Clinical Research Coordinator during Intake Interview
To ensure the quality of self-report data as all the measures are in English.

Current or past experience with CBT-I

Assessed with patient Hx
To evaluate why CBT-I was potentially unsuccessful in the past

No access to the computers, I-Pads, or the internet

Since the primary recruitment methods are via the internet, this is likely to be a non-issue.

c. Subject Recruitment

A broad strategy will be employed to recruit subjects so that our annual recruitment goals can be met or exceeded. The primary methods will be use of our volunteer database (presently more than 3500 individuals), ResearchMatch, Craigslist, and an Electronic Medical Records (EMR) query through the University of Pennsylvania Data Analytics Center (DAC). DAC EMR data consists of individuals diagnosed with Insomnia and/or individuals who have received one or more prescriptions for Insomnia. These strategies will be supplemented with local advertisements on cable TV, radio, city newspapers, local sleep centers, recruitment boards on Penn's campus, other community centers (e.g., senior citizen living centers), and

places of business (e.g., restaurants). All recruitment emails will be sent via REDCap's utility for group emails, and no individual will ever be contacted more than three times.

Additionally, compensation will be pro-rated for each component of the study for a total of \$500 per participant. Specifically, each participant will receive \$50 for completing the screening visit, \$25 for fully completing baseline sleep diaries, \$200 for fully completing all sleep diaries and questionnaires during the treatment period (8 weeks), \$100 for completing the study, and \$125 for completing the follow-up assessment.

d. Duration of Study Participation

All subjects will be monitored for 2 weeks prior to treatment, for 8 weeks during treatment, and for 2 weeks following treatment. Subjects receiving solriamfetol will take medication at 2pm daily for 4 weeks. Medication use will also include a 1-week placebo run-in and a 3-week placebo "run-out" (8 weeks' total). Additionally, follow-up questionnaires will be completed 3 months after end of treatment (Insomnia Severity Index [ISI] and Retrospective Sleep Continuity Assessment Questionnaire [RSCAQ]).

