"Subjects who withdraw consent to participate in the study will be asked to return their foil packs. Please see section 5g".

f. Early Termination Visits

See section; Subject Withdrawal

g. Subject Contact

Subjects will be contacted through phone, email, and via HIPAA compliant Zoom. Identifying information, such as names, will not be used.

Axsome Study - Table of Instruments						
Instrument Name	Abbreviation	Pre	Daily	Weekly	Post	Follow-up (3 mo.)
Sleep Disorder Symptom Checklist	SDS-CL-25	X			X	
Insomnia Severity Index	ISI	X		X	X	X
Retrospective Sleep Continuity Assessment Questionnaire	RSQAQ					X
Daily Sleep Diary	DSD		X			
Epworth Sleepiness Scale	ESS	X		X	X	
Brief Fatigue Inventory	BFI	X		X	X	
Functional Assessment of Chronic Illness Therapy – Fatigue Scale	FACIT-F	X		X	X	
PROMIS-SF 7a	PROMIS	X		X	X	
Functional Outcomes of Sleep Questionnaire	FOSQ-10	X				X
Profile of Mood State Questionnaire	POMS	X				X
Patient Health Questionnaire	PHQ-9	X		X	X	
Medical Symptom Checklist	MSCL	X		X	X	
Morin Insomnia Treatment Acceptability Scale	MITAS					X
Ecological Momentary Assessment	EMA		X			
Psychomotor Vigilance Test	PVT		X			

9. Study Evaluations, Measurements, and Schedule

a. Medical Record Review N/A

b. Physical Examination N/A. Physician Assent will be ascertained.

c. Vital Signs N/A. Physician Assent will be ascertained.

d. Laboratory Evaluations

The primary lab evaluation at screening is the Home Sleep Apnea Testing (HSAT, type 3 or 4 sleep study).

e. Pregnancy Testing

An effective method of birth control (as determined by their physician and intake) is required for women who are pre-menopausal. There are no requirements regarding the specific form of contraception that must be used. Subjects must agree to continue to use this method of birth control during the entire course of the study. If a subject does become pregnant during the study, they will be disenrolled. Outcome data on incidental pregnancies will not be collected.

f. Other Evaluations, Measures N/A

g. Efficacy Evaluations

The primary efficacy evaluation is accomplished with on-line prospective sampling, e.g., daily sleep diaries and the completion of weekly questionnaires.

h. Pharmacokinetic Evaluation N/A

i. Genetic Testing (only if applicable) N/A

j. Safety Evaluations

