Primary analyses will be conducted on an intention to treat basis and the trial conducted and reported according to CONSORT guidelines. Variable distributions will be examined to investigate homoscedasticity, outliers and normality, and corrected where appropriate using data transformations. The primary analysis is a 4(condition: +/- solriamfetol and +/- CBT-I) x 2(time: pre- and post-treatment) mixed ANOVA on absolute and percent change in total wake time ([TWT], time spent awake per night). If the interaction between condition and time is significant, Dunnett multiple comparisons will be conducted to further investigate differences in TWT between active treatment conditions versus the control condition to test Hypotheses 1-3. These analyses will be unadjusted in the first instance and then adjusted for covariates (primarily, age and sex).

An interim unadjusted analysis as per above will be conducted after 50% of the target sample have completed post-treatment (i.e., when N=20).

Secondary analyses include examining the interaction between treatment condition and time on other outcomes, including sleep continuity assessed via Sleep Diary (SL, WASO, EMA, TST, SE), insomnia (ISI), daytime sleepiness (ESS and KSS), fatigue (FSS and modified KSS), and daytime function (FOSQ-10, POMS, and PVT). Additionally, compliance to the medication (adherence to daily pill administration, as assessed via blister packs) and to sleep restriction (adherence to prescribed time to bed) will be investigated as covariates.

i. Baseline Data

Baseline and demographic characteristics will be summarized by standard descriptive statistics (including mean and standard deviation for continuous variables such as age and standard percentages for categorical variables such as gender).

ii. Pharmacokinetic Analysis **N/A**

iii. Interim Analysis **N/A**

iv. Safety Analysis

Side effects and adverse events will be assessed in several ways: daily assessments via the sleep diaries, and with a weekly evaluation using a medical symptoms checklist (52 symptoms where positive endorsements allow subjects to rate their average severity and number of days affected),

An adverse event will be defined as 1) any behavioral or health complaint spontaneously reported during the study, 2) an above threshold score on the study clinical assessment instruments (ESS, PHQ-9, or GAD-7), and/or a 20% increase in the medical symptom check list scores (frequency or severity).

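### FOSQ-10 and MITAS are weekly in section 4, but the instrument table gives FOSQ-10 and POMS no weekly or post-treatment mark and places MITAS only at 3 months, where the text allows only ISI and RSCAQ

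*Combined protocol and SAP*

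**What the plan says.** Section 4 (Investigational Plan) introduces a weekly battery: "Self-report weekly assessments will also be administered and will include standard retrospective measures of insomnia (ISI", followed by other scales. The list ends with MITAS for treatment acceptability "and daytime function (Functional Outcomes of Sleep-10 item, FOSQ-10". POMS is not mentioned in section 4.

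The Table of Instruments, under section 8.g, has five timing columns: "Instrument Name Abbreviation Pre Daily Weekly Post Follow-up (3 mo". The FOSQ-10 row carries two marks ("Functional Outcomes of Sleep Questionnaire FOSQ-10 X X"), which fall under Pre and Follow-up. POMS has the same two marks. MITAS has one mark, under Follow-up.

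For the 3-month contact, section 5.4 says that "subjects will complete two questionnaires (Insomnia Severity Index [ISI", the second being RSCAQ. Section 4 says the same. Section 6.d says "follow-up questionnaires will be completed 3 months after end of treatment" and names the same two instruments.

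Section 10.n names "daytime function (FOSQ-10, POMS, and PVT" among the secondary outcomes, to be examined through the interaction of treatment condition with time. The only time levels given in that section are pre- and post-treatment, and they are stated for the primary ANOVA on total wake time. The synopsis, section 5 and section 7.b describe the time factor as pre-post with follow-up data added.

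**The concern.** A questionnaire that is not put to subjects at the right visit cannot be recovered at analysis. Nothing in the protocol says whether the text or the table governs. The table is the only place that sets every instrument against every time point, so it is a natural source for the electronic forms.

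Daytime performance belongs to the secondary objective in section 3.2, and FOSQ-10 and POMS are two of the three measures that 10.n lists under daytime function. With the forms built from the table, an analyst would have baseline and, at best, a value three months after treatment ended. That value describes durability after both interventions have stopped. It does not answer the pre-post question.

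**Working it through.** No sample size or power figure bears on this point. The check is a comparison of schedules and a short timeline.

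**Step 1. The schedules side by side.**

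| Instrument | Section 4, during treatment | Table of Instruments | 3-month text (4, 5.4, 6.d) | Section 10.n |
|---|---|---|---|---|
| FOSQ-10 | Weekly | Pre, 3 months | Not listed | Daytime function |
| POMS | Not mentioned | Pre, 3 months | Not listed | Daytime function |
| MITAS | Weekly | 3 months | Not listed | Not named |
| ISI | Weekly | Pre, Weekly, Post, 3 months | Listed | Insomnia |
| RSCAQ | Not mentioned | 3 months | Listed | Not named |
| ESS | Weekly | Pre, Weekly, Post | Not listed | Sleepiness |

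The table therefore marks five instruments at 3 months (ISI, RSCAQ, FOSQ-10, POMS, MITAS) where the text allows two.

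**Step 2. Is the column reading sound?** ISI has separate marks at Post and at Follow-up. SDS-CL-25 is marked at Post and not at Follow-up. RSCAQ falls under Follow-up, where the text places it. All three rows fit the same five columns, and the FOSQ-10 row fits them with Weekly and Post empty.

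**Step 3. Values available per subject after baseline.** Section 4 has 8 treatment weeks and 2 post-treatment weeks, and does not say whether weekly forms stop at week 8. Weekly administration therefore gives 8 values, or 8 + 2 = 10 if it continues.

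| Source followed | FOSQ-10 before 3 months | FOSQ-10 at 3 months | POMS before / at 3 months | MITAS, all times |
|---|---|---|---|---|
| Section 4 text | 8 to 10 | 0 | 0 / 0 (not mentioned) | 8 to 10 |
| Table alone | 0 | 1 | 0 / 1 | 1 |
| Table to Post, text at 3 months | 0 | 0 | 0 / 0 | 0 |

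**Step 4. Timing of the only later value under the table.** Inputs from section 4: 1-week placebo run-in, 4 weeks active, 3-week placebo run-out, 2 weeks of monitoring afterwards. Three months after treatment is taken as 13 weeks.

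- Last active capsule: 1 + 4 = end of week 5.
- End of treatment: 5 + 3 = week 8, which is 8 − 5 = 3 weeks after the last active capsule.
- End of the post-treatment period: 8 + 2 = week 10, which is 10 − 5 = 5 weeks after it.
- Follow-up: 8 + 13 = week 21, which is 21 − 5 = 16 weeks after it and 13 weeks after the end of the treatment period.

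**The case against.** **The marks may have shifted.** The table is read from PDF text. Moving the FOSQ-10, POMS and MITAS marks one column left, to Post, would leave exactly ISI and RSCAQ at 3 months, as the text says, and would give FOSQ-10 and POMS a pre-post pair. This cannot be fully excluded, so the table in the protocol file should be checked first. It is not shown, however: the rows used as controls in step 2 align. Even with such a shift, the conflict between weekly in section 4 and no weekly mark in the table would remain for FOSQ-10 and MITAS.

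**Pre-post is not laid down for these outcomes.** A reader might infer that the plan fixes pre- and post-treatment as the time levels for FOSQ-10, so that its analysis becomes impossible for everyone. The documents do not go that far. Those levels are stated for the primary ANOVA, and the design descriptions add follow-up data to the time factor. A baseline-to-3-month interaction could be fitted under the table alone. What stands is that 10.n gives no other pair of levels, and that using the 3-month value contradicts three statements that the 3-month questionnaires are ISI and RSCAQ.

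**The secondary objective keeps its data.** A reader might also infer that daytime function is left unmeasured. It is not. FOSQ-10 and POMS are not named in the endpoint lists of sections 5.6.2 and 10; those lists cite ESS as an example of a daytime measure, and ESS is marked Pre, Weekly and Post. BFI, FACIT-F and PROMIS have the same marks, and EMA and PVT are marked Daily. This limits the importance of the point but does not remove it.

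**The worst case mixes two sources.** Having no value after baseline requires the table up to Post and the text at 3 months. That is correct, and it is why the loss is stated as conditional.

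**Conclusion.** The protocol contradicts itself on when FOSQ-10 and MITAS are given and on which questionnaires make up the 3-month battery, and it schedules POMS in a way that does not fit its analysis. The loss depends on which text the study team follows:

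- From the table, all 40 planned completers would have no FOSQ-10 or POMS value during or just after treatment, and the one later value would come about 16 weeks after the last active capsule instead of 3 or 5.
- With the 3-month text limit added, there would be no value after baseline for either, and no MITAS at all.
- From section 4, FOSQ-10 and MITAS would be collected weekly, but POMS has no scheduled value in the text.

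This rests on the column reading of the table, on 3 months being about 13 weeks from the end of the 8-week treatment period, and on pre-post being the intended contrast for these outcomes. That outcomes will certainly be lost does not follow from the documents. The primary endpoint is untouched. It is an inconsistency in the secondary outcomes that should be corrected, because data not collected cannot be restored later.

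**What to change.** First check the marks against the table in the protocol file. Then:

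- Mark FOSQ-10 and POMS at Post. This is what a pre-post analysis needs.
- Mark FOSQ-10 at Weekly too, so that the table agrees with section 4, as it already does for ESS.
- State in 10.n that the Post value is used for these two outcomes.
- Mark MITAS to match section 4.
- Make the 3-month column and sections 4, 5.4 and 6.d list the same instruments.

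The cost is a table and wording edit, with a few extra minutes of online questionnaires per subject within a battery that is already administered.
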